#### **2.3.4.1 ISIS 563580-CS1 Phase 1 SAD/MAD**

In a Phase 1 study, ISIS 563580-CS1, healthy volunteers received subcutaneous administration of ISIS 563580 from 50 to 400 mg as a single dose, or 100 to 400 mg as multiple doses (8 doses in 36 days). Overall, the safety findings from this study suggest that ISIS 563580 was not associated with any safety concerns. There were 383 adverse events (AE) reported in the ISIS 563580-treated subjects of which 363 (95%) were mild in severity. For the multiple-dose subjects, the most common treatment-emergent adverse events were AEs at the injection site. There was 1 serious adverse event (SAE) in the study of periorbital cellulitis which was considered a medically important event by the Investigator and was also considered unlikely related to Study Drug by the Investigator. Together, the above suggest that ISIS 563580 was well-tolerated at the doses and regimen given, which exceed the dose levels and cumulative exposures to be tested in the current study. There were no clinically-relevant changes in laboratory assessments and the heparin dose of 80 U/kg was well-tolerated in support of the post-heparin procedures. ISIS 563580 produced dose-dependent reductions in plasma ANGPTL3 (up to 93%; group means up to 84%), TG (up to 63%; group means up to 49%) and TC (up to 46%; group means up to 28%) at Day 36 (Brandt et al. 2015).

#### **2.4 Rationale for Dose and Schedule of Administration**

The Phase 1 program evaluated ISIS 703802 doses of 10 mg, 20 mg, 40 mg and 60 mg given weekly for 6 weeks that were found to be generally well-tolerated and to induce clinically-relevant reductions in lipid biomarkers. The range of dosing proposed for the present study will provide the equivalent drug exposure of 10 mg (from 40 mg monthly), and 20 mg (from 20 mg weekly and 80 mg monthly) administered weekly, and is predicted (based on modelling of PK/PD data obtained in Phase 1 study) to result in mean reductions from Baseline in TGs ranging from approximately 45 to 55% at steady-state.

Safety data from the available chronic mouse (26-week) and monkey (39-week) studies support once-weekly dosing for chronic administration. The No Adverse Effect Level (NOAEL) for ISIS 703802 in chronic monkey study was determined to be 12 mg/kg/wk.

Preclinical pharmacology experiments in Tg-mice and non-human primates demonstrated that ISIS 703802 achieved an equivalent reduction in ANGPTL3 plasma concentration to that of the unconjugated form, at 1/10th of the unconjugated ASO (ISIS 563580) dose.

## 2.5 Benefit-Risk Assessment

### 2.5.1 Benefit Assessment

The current study is designed to evaluate the safety and tolerance of ISIS 703802 in patients with hypertriglyceridemia, Type 2 Diabetes Mellitus (T2DM) and Nonalcoholic Fatty Liver Disease (NAFLD). The dose selected is expected to reduce ANGPTL3 and result in a reduction of triglyceride levels, reduction of fat content of the liver and improvement of glycemic control in T2DM patients. We do not know if subjects participating in this study would necessarily benefit from the treatment. However, the increased understanding of the effects of ISIS 703802 in this population may potentially result in new treatment options that would ultimately benefit patients with hypertriglyceridemia, T2DM and, NAFLD. Due to the short duration of this trial, any benefit observed is not expected to persist beyond the end of the study.

### 2.5.2 Risk Assessment

The known potential risks to study participants associated with ISIS 703802 are elaborated on in the Guidance to Investigator section of the Investigator's Brochure.

- In preclinical mouse studies, there were increases in ALT and AST and were correlated with increased incidence and/or severity of necrosis of individual hepatocytes (minimal to mild in severity). Those changes were most prominent in the high dose groups and showed no clear progression over time. No increases in liver enzymes were observed in monkeys from the 39-week toxicity study up to 12 mg/kg/week (~200-fold of the 20 mg clinical dose by plasma AUC). In the 16-week monkey study, increase in ALT was only evident in 1 early-sacrifice animal at 35 mg/kg/week, no meaningful increase in ALT was observed in the schedule sacrificed animals.
- One subject in the 60 mg weekly dose cohort had an approximately 5 x ULN increase of ALT, without increase in bilirubin, which was considered a treatment related adverse event (AE) by Principal Investigator (PI) a second subject had an ALT of 88 U/L on Day 36 post treatment which returned to normal range by Day 50 and remained normal until the end of the study. There were no other observed clinically significant changes in ALT and liver function in an ongoing Phase 1 human study (data on file).
- However, to evaluate and mitigate the potential for liver enzyme abnormalities, regular liver chemistry monitoring and stopping rules are included in the study as specified in [Sections 8.5 and 8.6](#).
- Injection site adverse events, while not considered safety issues, may affect the ability of the subject to tolerate dosing. Injection site adverse events are the most common side

effects observed following SC administration of 2'-MOE ASOs and are dose and concentration dependent. Erythema is the most prevalent characteristic. Generally, these events are mild and reversible, resolve spontaneously and do not worsen with time. The histologic findings are consistent with a local inflammatory response. Subjects should be informed of the possibility of occurrence of injection site adverse events. Symptomatic interventions such as icing of the injection site or administration of NSAIDs prior to and/or after the SC dosing have been utilized.

- Although no changes in platelet (PLT) counts have been observed in healthy volunteers, mouse or monkey in both sub-chronic and chronic studies with ISIS 703802, reductions in platelet counts to below the lower limit of normal have been observed after administration of other ASOs and some subjects have experienced severe thrombocytopenia following administration of unconjugated 2'-MOE ASOs. To evaluate and mitigate the potential for a reduction in PLT count, monitoring and stopping rules are included in the study as specified in [Sections 8.5 and 8.6 \(Safety Monitoring Rules and Stopping Rules\)](#).
- No significant changes in serum creatinine, electrolytes, BUN, or urinalysis were reported from the interim analysis of the ongoing Phase 1 study (data on file). To evaluate and mitigate the potential for a reduction in renal function, since kidneys are an organ of high distribution for the studied ASO, monitoring and stopping rules are included in the study as specified in [Sections 8.5 and 8.6 \(Safety Monitoring Rules and Stopping Rules\)](#).

While the long-term effects of reducing ANGPTL3 as a target with the Study Drug are not known at this time, there is evidence in literature in humans in whom ANGPTL3 is absent from plasma, due to homozygous or compound heterozygous ANGPTL3 mutations, present a pan-hypobetalipoproteinemia phenotype, with generalized and marked decreases (~50% to 70%) in all apoB-100 containing lipoproteins, including VLDL and LDL, as well as HDL. This clinical phenotype has been termed familial combined hypolipidemia or FHBL2 ([Romeo et al. 2009](#); [Musunuru et al. 2010](#); [Martin-Campos et al. 2012](#); [Minicocci et al. 2012](#); [Noto et al. 2012](#); [Pisciotta et al. 2012](#); [Wang et al. 2015](#)). Clinical studies in FHBL2 suggest a trend toward lower glucose and insulin levels and reported a decrease in VLDL. Remarkably, diabetes and cardiovascular disease are reportedly absent from those with homozygous FHBL2 and, no adverse clinical phenotype has been reported to date.

### **2.5.3 Overall Assessment of Benefit: Risk**

ISIS 703802 has demonstrated the ability to reduce ANGPTL3, APOCIII, and TGs by greater than 60% in the Phase 1 study in healthy volunteers. The objective of this study is to assess the effect of TG lowering in these subjects. This study will also investigate the potential of ISIS 703802 in improving the insulin resistance and glucose profile, and decreasing liver and visceral fat content in subjects with high TG levels and T2DM. Although the subjects enrolled in this study will not derive long term benefits due to the short duration of the study, they may derive some short term benefit from improved metabolic health and dietary counselling. The information obtained in the course of this study is critical to further development of ISIS 703802 for hypertriglyceridemia, dyslipidemia, NAFLD and associated metabolic complications and cardiovascular disease.

The protocol identifies that potential risks associated with ISIS 703802 treatment will be mitigated by routine monitoring. Thus, exposure of subjects in this study is justified by the anticipated benefits that may be afforded to the wider population of patients by continued development of ISIS 703802 (see [Section 8.5 Safety Monitoring Rules](#)).

### 3. EXPERIMENTAL PLAN

#### 3.1 Study Design

This is a Phase 2 multicenter, randomized, double-blind, placebo-controlled, dose-ranging study. Approximately 96 subjects will be randomized in a 3:1 ratio to receive ISIS 703802 or placebo. The sample size was determined to provide statistical power for efficacy assessments. Study Drug (ISIS 703802 or placebo) will be administered SC every week or every 4 weeks, depending on cohort assignment, for 26 weekly doses, or 6 every 4-week doses.

Subjects will be evaluated for study eligibility during Screening and Qualification, which takes place up to 5 weeks prior to Day 1 (the first day of Study Drug administration). During the Screening Period, subjects will be advised to maintain routine diet and exercise routines and remain on a stable regimen of diabetes and lipid medications (if they are already taking any). As part of the Screening Period, following 4 weeks of diet run-in, subjects will have a qualification visit and, final eligibility assessments will be performed. Subjects on a stable diet known to the investigator and followed at the site may go from Screening to qualification without a 4-week diet run-in. At the qualification visit, TGs will be measured to qualify ( $\geq 150$  mg/dL). MRI will be obtained during screening once all other eligibility criteria are met to assess liver fat content.

Subjects meeting eligibility criteria at Screening and having a qualifying MRI, defined as having greater than 8% liver fat assessed by MRI-PDF (via central reviewer) will return to the clinic on Day 1. TG and MRI results must be available prior to randomization and administration of the first dose of Study Drug. Subjects who continue to meet all eligibility criteria at Day 1 will be randomized to 1 of the 3 dosing cohorts, with each cohort having a 3:1 ratio to receive ISIS 703802 or matching volume of placebo, respectively, by SC injection.

The primary safety and efficacy analysis time point is at Week 27 for subjects who received weekly dosing (Cohort A) and at Week 25 for subjects who received every 4-week dosing (Cohorts B and C).

Cohort A (n = 32): 20 mg ISIS 703802 or placebo (3:1) SC once every week for 26 doses.

Cohort B (n = 32): 40 mg ISIS 703802 or placebo SC (3:1) once every 4 weeks for 6 doses.

Cohort C (n = 32): 80 mg ISIS 703802 or placebo SC (3:1) once every 4 weeks for 6 doses.

Subjects will return regularly for outpatient visits throughout the treatment period according to the Schedule of Procedures ([Appendix A](#)).

Subjects will then enter a 13 week Post-Treatment Follow-up Period and will return to the Study Center for outpatient evaluations according to the Schedule of Procedures ([Appendix A](#)).

Blood and urine samples will be collected regularly throughout the study for safety, efficacy, and PK analysis. [Appendix B](#) shows a list of analytes required for the study and [Appendix C](#) details the PK sample schedules.

### **3.2 Number of Study Centers**

This is a multicenter, multinational study.

### **3.3 Number of Subjects**

Approximately 96 subjects are planned to be enrolled in this study.

Approximately 32 subjects will be assigned to each cohort, with 24 subjects receiving ISIS 703802 and 8 receiving placebo.

### **3.4 Overall Study Duration and Follow-up**

The length of subjects' participation in the study will be up to 44 weeks, including an up to 5-week Screening Period, that includes a 4-week diet stabilization/run-in period for subjects not already on a stable diet, and a 1-week qualification period, a 26-week treatment period, and a 13-week post-treatment evaluation period. Please refer to the Schedule of Procedures in [Appendix A](#).

Subjects may be required to attend additional visits for monitoring of adverse events or abnormal investigation results. The frequency of additional monitoring will be determined by the Study Medical Monitor in consultation with the Investigator.

#### **3.4.1 Screening**

Subject eligibility for the study will be determined within 35 days/5 weeks prior to randomization. Potential subjects will report to the Study Center for screening/qualification assessments at specified intervals within the 5-week Screening Period as detailed in the Schedule of Procedures in [Appendix A](#).

#### **3.4.2 Treatment**

Eligible subjects will receive the first dose of Study Drug at the Study Center, at which time they will also be trained on self-administration of Study Drug, if applicable. Subsequent administrations of Study Drug may occur at home or at the Study Center. Eligible subjects will report to the Study Center for assessments at specified intervals throughout the 26-week treatment period as detailed in the Schedule of Procedures in [Appendix A](#).

#### **3.4.3 Post-Treatment**

After the dosing with Study Drug is completed, subjects will then enter the 13-week post-treatment follow-up period and will return to the Study Center for 3 follow-up visits according to the Schedule of Procedures in [Appendix A](#).

The final study visit for each subject will be 13 weeks after the Treatment Period (last dose through one dosing interval post last dose).

### **3.5 End-of-Study**

The End-of-Study is defined as the last subject's last visit.

### **3.6 Data and Safety Monitoring Board**

An independent Data and Safety Monitoring Board (DSMB) will be assembled to review safety, tolerability and efficacy (as needed) data collected on ISIS 703802 during this study. Based on its ongoing assessment of the safety and tolerability of ISIS 703802, the DSMB will provide recommendations to the Sponsor for modifying, stopping or continuing the study as planned. Details on the safety assessments, frequency of review, meeting schedules and controlled access to unblinded data are outlined in the DSMB Charter and Statistical Analysis Plan (SAP).

## **4. SUBJECT ENROLLMENT**

### **4.1 Screening**

Before subjects may be enrolled into the Study, the Sponsor or designee requires a copy of the Study Center's written independent ethics committee/institutional review board (IEC/IRB) approval of the protocol, informed consent form, and all other subject information and/or recruitment material.

Subjects must sign the informed consent form before any screening tests or assessments are performed. At the time of consent, the subject will be assigned a unique screening number before any study procedures, including screening procedures, are performed. This number will be used to identify the subject throughout the trial and must be used on all study documentation related to that subject. At the time of randomization, subjects will be assigned a unique randomization number. The subject identification number must remain constant throughout the entire trial. Subject identification numbers and randomization numbers, once assigned, will not be reused.

### **4.2 Randomization**

Subjects will be randomized after all screening and qualification assessments have been completed and after the Investigator has verified that they are eligible per criteria in [Sections 5.1](#) and [5.2](#). No subject may begin treatment prior to randomization and assignment of a unique subject identification number.

Using an Interactive Web-Response System (IXRS), eligible subjects will be randomized in a 1:1:1 ratio to 1 of the 3 parallel-dose cohorts (Cohorts A, B, or C). Within each dose cohort, subjects will be randomized in a 3:1 ratio to receive ISIS 703802 or matching volume of placebo, respectively.

A permuted block schedule will be used. The randomization schedule will be generated and held by an independent vendor.

### **4.3 Replacement of Subjects**

Subjects who withdraw from the study will not be replaced.

#### 4.4 Unblinding of Treatment Assignment

All subjects, monitors, and Study Center personnel related to the study will be blinded throughout the study and until all subjects have completed the study and the database has been locked. The Sponsor will be blinded throughout the study and until all subjects have completed the treatment period. However, if a subject has suffered a SAE (as defined in [Section 9.3.3](#)), and/or when knowledge of the treatment assignment will impact the clinical management of the subject, the Investigator will have the ability to unblind the treatment assignment for that subject using the IXRS. The Sponsor will determine the point at which all treatment assignments will be unblinded. The Sponsor or designee will be informed of the unblinding of a subject within 24 hours. In addition, all SUSARs will be unblinded by the Sponsor's or designee's Drug Safety and Quality Assurance personnel for the purpose of regulatory reporting (see [Section 9.2](#)).

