## 8.5 Safety Monitoring Rules

Please refer also to the “Guidance for Investigator” section of the Investigator’s Brochure.

For the purposes of safety monitoring, Baseline is defined as the average of the pre-dose test closest to Day 1 and the Day 1 value itself.

In addition to the standard monitoring of clinical safety parameters, the following guidelines are provided for the monitoring of selected parameters chosen based on preclinical and clinical observations.

In case of discrepancy between the test results from 2 sources, such as between the central and local lab, safety-mandated action must be initiated based on the more critical (lower or higher, as relevant) of the 2 values.

**Confirmation Guidance:** At any time during the study (treatment or post-treatment follow-up periods), the clinical laboratory results meeting any of the safety monitoring criteria presented below **must be confirmed** by performing measurements (ideally in the same laboratory that performed the initial measurement) on new specimens prior to administering the next dose of Study Drug (ISIS 703802 or placebo). All new specimen collections should take place as soon as possible (ideally within 3 days of the initial collection).

In addition, as described in [Section 6.2](#) hematology labs should be sent in parallel to the central and local laboratory for analysis.

**Stopping Rule Guidance:** The Investigator may interrupt or permanently discontinue study treatment for any medical reason including changes in clinical laboratory results.

In the event of an initial clinical laboratory result that meets a stopping criterion, subjects must not be re-dosed until a confirmatory test result has been reviewed by the Study Medical Monitor. If any of the stopping criteria described below are met and are confirmed, the subject will be permanently discontinued from further treatment with Study Drug (ISIS 703802 or placebo), evaluated fully as outlined below and in consultation with the Study Medical Monitor or appropriately qualified designee, and will be entered into the post-treatment evaluation portion of the study. In general, subjects who do not meet the stopping rules based upon retest may continue dosing. However, the Investigator and the Study Medical Monitor (or appropriately qualified designee) should confer as to whether additional close monitoring of the subject is appropriate.

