If none from the above-mentioned reason can be found, or if appropriate action fails to decrease blood glucose/HbA1c under the threshold values, rescue medication may be introduced at the Investigator discretion and according to local guidelines.

All assessments for primary and secondary efficacy and safety parameters planned in final primary endpoint assessment visit should be performed before adding the rescue medication if possible. Then the subject continues the study treatment and stays in the study in order to collect safety information. The planned visits and assessments should occur until the last scheduled visit. (See more details in [Appendix A](#)).

Note: After Study Drug discontinuation any treatments are permitted, as deemed necessary by the Investigator.

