### **9.2 Regulatory Requirements**

The Sponsor or designee is responsible for regulatory submissions and reporting to the Investigators of serious adverse events (SAEs) including suspected unexpected serious adverse reactions (SUSARs) per the International Conference on Harmonization (ICH) guidelines E2A and ICH E6. Country-specific regulatory requirements will be followed in accordance with local country regulations and guidelines.

Institutional Review Boards (IRB)/Independent Ethics Committees (IEC) will be notified of any SAE according to applicable regulations. The Data and Safety Monitoring Board (DSMB) will be notified of any SAE as specified in the DSMB charter.

In addition to the Investigator's assessment of relatedness, the Sponsor or designee will evaluate the available information and perform an independent assessment of relatedness. While the Sponsor may upgrade an Investigator's decision, it is not permissible to downgrade the Investigator's opinion for the purposes of determining whether the SAE meets the definition of a SUSAR.

Appropriate personnel at the Sponsor or designee will unblind SUSARs for the purpose of regulatory reporting. The Sponsor or designee will submit SUSARs to Regulatory Agencies in blinded or unblinded fashion according to local regulation. The Sponsor or designee will submit SUSARs to Investigators in a blinded fashion.

For the purpose of regulatory reporting of SUSARs, there are no "expected" AEs in this study population. For Study Drug (ISIS 703802 or placebo) "expected" AEs, refer to the Investigator's Brochure.

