### **9.3.3 Serious Adverse Event (SAE)**

A serious adverse event is any adverse event that in the view of either the Investigator or Sponsor, meets any of the following criteria:

- Results in death
- Is life threatening: that is, poses an immediate risk of death at the time of the event  
An AE or suspected adverse reaction is considered “life-threatening” if, in the view of either the Investigator or Sponsor, its occurrence places the subject at immediate risk of death. It does not include an AE or suspected adverse reaction that, had it occurred in a more severe form, might have caused death
- Requires inpatient hospitalization or prolongation of existing hospitalization  
Hospitalization is defined as an admission of greater than 24 hours to a medical facility and does not always qualify as an AE
- Results in a persistent or significant incapacity or substantial disruption of the ability to conduct normal life functions
- Results in a congenital anomaly or birth defect in the offspring of the subject (whether the subject is male or female)
- Important medical events that may not result in death, are not life-threatening, or do not require hospitalization may also be considered serious when, based upon appropriate medical judgment, they may jeopardize the subject and may require medical or surgical intervention to prevent one of the outcomes listed in this definition. Examples of such medical events include allergic bronchospasm requiring intensive treatment in an emergency room or at home, blood dyscrasias or convulsions that do not result in inpatient hospitalization, or the development of drug dependency or drug abuse

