#### **9.4.3 Evaluation of Adverse Events (Serious and Non-Serious)**

The Investigator's opinion of the following should be documented on the Adverse Event Case Report Form.

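### Protocol Section 4.4 makes an SAE alone enough for the Investigator to break the blind, even when the allocation does not affect care, which can bias that subject's relatedness ratings

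*Protocol*

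**What the plan says.** Protocol Section 4.4 sets the general rule that subjects, monitors and site staff stay blinded until everyone has finished and the database is locked. The exception has two limbs. The first is "if a subject has suffered a SAE", with a pointer to the definition in Section 9.3.3. The second follows directly: "and/or when knowledge of the treatment assignment will impact the clinical management of the subject, the Investigator will have the ability to unblind" that subject in the IXRS. The only control stated for such a break is notice afterwards: "The Sponsor or designee will be informed of the unblinding of a subject within 24 hours".

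The SAE definition in Section 9.3.3 does not depend on cause. One of its criteria reads "Requires inpatient hospitalization or prolongation of existing hospitalization".

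The Investigator's part in the safety data is set out elsewhere in the protocol:

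- **Causality and severity** (Section 9.4.3): the Investigator's "opinion of the following should be documented on the Adverse Event Case Report Form".
- **Interruption and discontinuation** (Section 8.5): "The Investigator may interrupt or permanently discontinue study treatment for any medical reason including changes in clinical laboratory results".
- **Rescue** (Section 8.5.7), once thresholds are exceeded and other explanations or actions are exhausted: "rescue medication may be introduced at the Investigator discretion and according to local guidelines".

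On SUSARs, Section 9.2 states: "The Sponsor or designee will submit SUSARs to Investigators in a blinded fashion".

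**The concern.** A code-break rule defines who may see an allocation and for what reason. The accepted reason is that the subject's care depends on it, and the second limb of Section 4.4 covers that case in full. The SAE limb therefore adds only access that care does not require.

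That access goes to the person who judges causality. Protocol Section 9.4.3.1 offers four relationship categories and groups Unlikely/Remote with Not Related for reporting. SAP 3.5.1 counts Related, Possible and missing as related. Moving a rating between Possible and Unlikely/Remote therefore moves an event into or out of the related-TEAE and related-SAE tables. An Investigator who knows the subject is on active drug, or on placebo, may rate differently. AEs are recorded until the end of follow-up (Section 9.4.2), so the knowledge also reaches later ratings in that subject.

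The data exposed count in a decision. The Synopsis, under Statistical Considerations, lists the incidence of treatment-related SAEs among the safety grounds for choosing a dose.

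**Working it through.** The plan gives no figure on this point, so the check is mainly a reading of the text, followed by a bound on size.

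**1. What the connective does.** There are four possible situations:

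| SAE? | Allocation needed for care? | Section 4.4 as written | If need were the only condition |
|---|---|---|---|
| Yes | Yes | Break allowed | Break allowed |
| Yes | No | Break allowed | Not allowed |
| No | Yes | Break allowed | Allowed |
| No | No | Not allowed | Not allowed |

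Only the second row differs. No medically needed break depends on the SAE limb.

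**2. Whether another passage narrows the SAE limb.** Section 9.3.3 defines an SAE regardless of relatedness. It adds that an admission over 24 hours is not always an AE, and Section 9.5.2 excludes documented prescheduled or elective procedures. These trim the definition but do not add a test of need. Section 9.2 covers SUSAR unblinding by Sponsor safety personnel, not Investigator code breaks. SAP 2.4 withholds lipid, ANGPTL3, PK, selected PD and MRI results from sites, but does not govern the IXRS. I found no requirement in either document for a recorded reason or for causality to be rated before the break, and no SAP rule for data recorded after one.

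**3. Which data are exposed.**

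- *Exposed:* relatedness and severity ratings; interruption for medical reasons; the final rescue decision.
- *Largely constrained:* the liver, renal and platelet stopping rules (8.6.1 to 8.6.3) are mostly numeric. Platelet dose changes follow Table 3, and other dose changes involve the Medical Monitor (8.6.4, 8.7). Rescue is considered only after glucose or HbA1c thresholds are passed (8.5.7).
- *Not materially exposed:* fasting triglycerides, taken from the central laboratory (SAP Table 1) and masked to Investigators after randomization (SAP 2.4).

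**4. Size.** Inputs: N = 96 subjects, 24 per analysis group (Protocol 10.2). The SAE proportion p is not given for this trial, so 3% to 10% is assumed.

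Subjects eligible on the SAE limb = N × p:

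- 96 × 0.03 = 2.9
- 96 × 0.05 = 4.8
- 96 × 0.10 = 9.6

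Per group of 24: 24 × 0.03 = 0.7, and 24 × 0.10 = 2.4.

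Needless code breaks = N × p × u, where u is the share of those subjects who are in fact unblinded without need. The documents say nothing about u, which lies between 0 and 1. Over the assumed range of p, the count lies between 0 and about 10.

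For scale, one subject moved into or out of the related-SAE count changes a group's proportion by 1/24 = 4.2 percentage points.

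**The case against.** The strongest reply is that Section 4.4 grants an ability and imposes no duty. Many Investigators would not use it without need, and some SAEs would meet the clinical-need limb anyway. That stands: the number of needless breaks could be close to zero. The only SAE data in the documents are from short Phase 1 studies. The interim analysis of this drug in 44 subjects recorded none (Protocol 2.3.4), and the study of the unconjugated parent drug recorded one (2.3.4.1). Those subjects and durations differ from this trial, so they do not supply its rate, but they give no reason to expect a high one.

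Second, there are safeguards. The Sponsor makes its own relatedness assessment of SAEs (9.2), is told of any break within 24 hours, and is itself blinded through the treatment period. This limits the consequence. However, Section 9.2 concerns regulatory reporting and bars downgrading the Investigator's opinion when SUSAR status is decided. The SAP does not say that the Sponsor's rating replaces the Investigator's in the tables. SAP 3.5.1 also tabulates all TEAEs and SAEs regardless of relatedness, so only the related subset depends on these ratings. Platelet reductions, another dose-selection criterion, are laboratory based.

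Third, a reader might infer that Section 4.4 defeats the blinded SUSAR distribution in Section 9.2. It does not. Section 9.2 stops allocations being sent to Investigators generally, while Section 4.4 concerns one Investigator and one subject. The two fit together poorly but do not contradict each other.

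Fourth, making need the only condition does not remove bias from ratings made after a break that is needed. That is correct, and is why the order of recording belongs in the fix.

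**Conclusion.** The wording point holds. An SAE of any cause is a sufficient trigger, nothing else in the protocol or SAP narrows it, and it adds no access that patient care requires. It opens an avoidable route to unblinded relatedness ratings and, to a lesser degree, to unblinded interruption and rescue decisions for the subject concerned.

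The size is unknown. About 3 to 10 subjects would be eligible on this limb if 3% to 10% of 96 have an SAE. The rate is an assumption, and the count is an upper bound on needless breaks, not a forecast.

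Three stronger conclusions might be drawn, and the documents do not support them:

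- *That the safety comparison is biased.* Bias is possible; none is shown, and its direction and amount cannot be derived.
- *That an unblinded Investigator would control dosing and rescue.* Numeric rules and Medical Monitor involvement leave limited discretion.
- *That the efficacy result is at risk.* SAP Sensitivity Analysis 4 does treat discontinuation for AE or lack of efficacy differently, so a recorded reason could matter there. It is a supporting analysis, and the primary endpoint is a masked central-laboratory value.

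This is a modest, inexpensive improvement to the blinding rule. It does not threaten the primary conclusion.

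**What to change.** Reword the exception in Protocol Section 4.4 along these lines: *The Investigator may unblind a subject in the IXRS only when, in the Investigator's judgement, that subject's clinical management requires the allocation to be known, for example after an SAE. Where time allows, the reason for the break and the causality rating of the event are recorded first.*

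Keep the Investigator's immediate IXRS access, the Investigator as sole judge of need, and the 24-hour notice to the Sponsor. Leave SUSAR unblinding by Sponsor safety personnel as written. No dosing, stopping or rescue provision changes.

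The cost is a minor protocol amendment, handled under Section 12.1 with Investigator agreement and notice to the regulator and the IEC/IRB, plus a brief documentation step at the site. The added question of need arises while an SAE is being managed. It should not delay care, because the Investigator answers it alone and the recording step gives way when time is short.
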